NCT04349371

Title: Chloroquine (CQ) prophylaxis for Health Care Workers at risk for COVID

Short title: Saved by CQ

Clinical Phase: II

PI: [name] MPH

Co-investigator: [name] MPH

Protocol Version: 3.0 (IRB approved 11/09/2020)

**Primary Objective:** The primary objective is to determine the clinical efficacy of CQ in health care workers with moderate to high risk of exposure to COVID-19 in preventing symptomatic COVID-19 infections.

**Secondary Objectives:** Secondary endpoints will explore the efficacy of CQ in preventing any infection as defined by seroconversion to positive anti-COVID antibody status.

**Study Design:** Double blind, placebo controlled, randomized study of CQ in health care workers with risk of COVID exposure. The primary objective is to determine the clinical efficacy of CQ in health care workers with moderate to high risk of exposure to COVID-19 in preventing symptomatic COVID-19 infections. Safety assessments include AEs, vital signs, ECGs, and physical examinations.

Stratification will be based and levels of exposure: -moderate risk: defined by patient facing work in outpatient/in-house clinic at least 2 days/week -high risk: ICU/ER/procedure rooms with aerosolized particles and high risk of contamination Stratification based on age: -Under 50 years of age -Older than 50 years of age

**Sample size:** 175 patients/group. Sample size based on a projection that 15% of healthcare workers will develop symptomatic COVID-19 illness and an anticipated 67% reduction in rate (i.e. 5%) among those treated with CQ. 175 patients per group, allowing for a 10% dropout rate, will permit detection of a difference of this magnitude or greater for the primary endpoint, assuming a two-tailed alpha and 80% power. The trial is not powered on any secondary outcomes or interim analyses.

**Study Duration:** -1 month accrual of patients with treatment duration of 2-3 months or until exposure levels become negligible - 2 month follow up visit, 3 month follow up visit

**Treatment Description:** 3 Patients will receive CQ 500 mg every day for one week, then 500 mg weekly for the duration of the exposure. A dose of 250 mg daily will be allowed for severe GI intolerance.

**Primary Endpoint:** Decrease by 67% in number of symptomatic illness in at risk healthcare workers; a decrease in symptomatic COVID infections from 15% to 5% in the treatment arm.

**Co-primary Endpoint:** Decrease by 70% in number of severe illness in at risk healthcare workers.

**Secondary Endpoints:** 1. Decrease by 67% in number of sero-conversions in at risk healthcare workers. 2. Percent of patients with adverse events NCI-CTCAE Grade 3 or higher. 3. Percent of patients with GI intolerance.

**Inclusion Criteria:** 1) Age  $\geq$ 18 years, 2) Employment by New York Presbyterian Hospital 3) Clear assignment to areas of the hospital that involve patient contact and possible exposures for at least 2 days a week  $\geq$  8 hours a day

**Exclusion Criteria:** 1) Individuals who are taking CQ for other indications 2) New use of NSAIDs 3) High risk background medications not limited to immunosuppressive regimens, steroids, anti-B cell therapies, anti-cytokine therapies, chemotherapies, JAK-inhibitors 4) Individuals with a history of retinopathy that would contraindicate the use of CQ 5) Known allergy to CQ or chloroquine 6) Known QT prolongation and torsades de point 7) Have screening electrocardiogram (ECG) abnormalities that, in the opinion of the investigator, are clinically significant and indicate an unacceptable risk for the patient's participation in the study. 8) Any individual with QTc over 500 msec will be excluded. 8) Individuals who have history of any cardiac disease. 9) Individuals with history of renal disease 10) Individuals who are taking any QT prolonging meds such as but limited to: • Antipsychotics: Haloperidol, Ziprasidone, Quetiapine, Thioridazine, Olanzapine, Risperidone • Antiarrhythmics: Amiodarone, Sotalol, Dofetilide, Procainamide, Quinidine, Flecainide • Antibiotics: Macrolides, Fluoroquinolones • Antidepressants: Amitriptyline, Imipramine, Citalopram, • Others: Methadone, Sumatriptan, Ondansetron, Cisapride

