### **Study Stopping Rules**

Study enrollment will be put on temporary hold and expedited reports will be prepared and reported to the DSMB for an ad hoc meeting if any the following occur: 1) Severe GI intolerance to chloroquine 2) Anaphylactic/high risk reaction to chloroquine 3) Symptomatic COVID-19 infection 4) QT prolongation and torsades de point that, in the opinion of the investigator, are clinically significant and indicate an unacceptable risk for the patient's participation in the study. 2) The occurrence of NCI-CTCAE Grade 3 or higher adverse events (including serious adverse events) that are related to study drug in 1 of the first 6 subjects, 2 of the first 23 or 3 of the first 45 or 5 subjects at any time. (It is estimated that the prevalence of Grade 3 or higher adverse events in the placebo group will be about 1 percent.), 3) At the request of the DSMB. The DSMB may only stop the trial for safety concerns. DSMB members: [name], [name], [name]. The DSMB will meet monthly to evaluate any safety and unforeseen protocol issues.

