### **ECG**

Per the Food and Drug Administration Emergency Use Authorization guidelines with respect to chloroquine, a single 12-lead standard ECG will be obtained locally at Visit 1 and read by a qualified physician (the investigator or qualified designee) at the site to determine whether the patient meets entry criteria. However if the subject had received an ECG test within the past 12 months and no abnormalities were found, the ECG does not have to be obtained. An ECG test will be administered at the end of the study. Electrocardiograms may be obtained at additional times, when deemed clinically necessary. If the patient presents with unanticipated ECG findings, they will be referred to a cardiology specialist immediately. Patients with QTc between 460-500 msec will be reviewed with a Cardiologist before initiating treatment. Randomization: Randomization to the study drug versus the placebo will be performed in a 1:1 fashion. Simple randomization without blocking or stratification will be followed, with treatment allocation according to a pre-specified computer-generated randomization list provided to the research pharmacy. Blinding: Randomization will be accomplished by the Research Pharmacy, which will provide the study drug and the placebo in identical pill bottles. This will ensure double-blinding to both participants and the study team. In case of an emergency, the investigator has the sole responsibility for determining if unblinding of a patient's treatment assignment is warranted.

Patient safety must always be the first consideration in making such a determination. If the investigator decides that unblinding is warranted, the investigator should make every effort to contact the Research Pharmacy prior to unblinding a patient's treatment assignment unless this could delay emergency treatment of the patient. All calls resulting in an unblinding event are recorded and reported to the IRB. If an investigator, site personnel performing assessments, or patient is unblinded, the patient must be discontinued from the study unless there are ethical reasons to have the patient remain in the study.

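### The 250 mg daily allowance for severe GI intolerance is not tied to a dosing phase: in week 1 it halves the daily amount, but in the weekly phase it gives 3.5 times the weekly amount

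*Combined protocol and SAP*

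**What the plan says.** The Treatment Description in the combined protocol and SAP has two dosing sentences. The first gives the standard regimen: "500 mg every day for one week, then 500 mg weekly for the duration of the exposure". The second gives the exception: "A dose of 250 mg daily will be allowed for severe GI intolerance".

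Study Duration gives a "treatment duration of 2-3 months or until exposure levels become negligible".

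The exception has no phase, no start day, no length and no instruction on what follows it. The only other section that takes severe GI intolerance as a condition is the Study Stopping Rules, where "Severe GI intolerance to chloroquine" is one of several events that trigger a hold on enrollment. That section states no dose.

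**The concern.** The exception directly follows a sentence that covers two phases with very different weekly amounts, and severe GI intolerance can arise in either. A fixed daily amount of 250 mg is below the standard daily amount in the first phase. Taken every day in the second phase, it adds up to more than the standard weekly amount. The same sentence therefore lowers or raises weekly exposure depending on when it is used.

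The gap remains even for a reader who starts the exception in week 1. From day 8 the standard regimen is weekly, and the text does not say whether a participant on 250 mg daily then moves to the weekly schedule or continues daily.

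At stake is how much drug is taken by participants who have already reported severe intolerance, and whether they are all handled alike. Two staff members could follow the text faithfully and give different schedules. The weekly phase is also most of the treatment period: 7 of 8 weeks to 12 of 13 weeks, if treatment lasts 8 to 13 weeks.

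**Working it through.** The plan states no cumulative dose or ratio, so there is no figure of its own to reproduce. What follows is direct dose arithmetic.

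**Inputs**

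- Standard regimen (Treatment Description): 500 mg daily for 7 days, then 500 mg per week.
- Exception (Treatment Description): 250 mg daily, or 7 × 250 = 1,750 mg per week.
- Treatment length *w* (Study Duration): 2 to 3 months, taken here as 8 to 13 weeks. This is an assumption, and treatment may end sooner if exposure becomes negligible.

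**Step 1. Standard course.** Total = 3,500 + 500(*w* − 1).

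- *w* = 8: 3,500 + 3,500 = 7,000 mg
- *w* = 13: 3,500 + 6,000 = 9,500 mg

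**Step 2. Exception used in week 1.** Let *k* be the number of 500 mg doses taken before the switch (0 to 6). The week-1 total is 500*k* + 250(7 − *k*), and its ratio to 3,500 mg is 0.5 + *k*/14.

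- *k* = 0: 1,750 mg, ratio 0.50
- *k* = 6: 3,250 mg, ratio 0.93

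From the switch onward the daily amount is halved. The documents do not fix *k*, so the whole range applies.

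**Step 3. Exception used in a week of the weekly phase.** 1,750/500 = 3.5, an excess of 1,750 − 500 = 1,250 mg for each such week. Each single dose is 250 mg in place of 500 mg.

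**Step 4. Whole course, by how the exception is used.**

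| Use of the exception | 8 weeks (standard 7,000 mg) | 13 weeks (standard 9,500 mg) |
|---|---|---|
| Week 1 only, from day 1 | 5,250 mg (0.75) | 7,750 mg (0.82) |
| Week 1 only, on day 7 alone | 6,750 mg (0.96) | 9,250 mg (0.97) |
| One week of the weekly phase, then back to weekly | 8,250 mg (1.18) | 10,750 mg (1.13) |
| Daily to the end, from day 1 | 14,000 mg (2.00) | 22,750 mg (2.39) |
| Daily to the end, after a full standard week 1 | 15,750 mg (2.25) | 24,500 mg (2.58) |

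Use confined to week 1 gives about 0.75 to 0.97 times the standard course. Daily use to the end, begun in or right after week 1, gives about 2.0 to 2.6 times. A later start, or an earlier return to weekly dosing, gives less.

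**Step 5. Short treatment.** If the exception starts in week 1 and simply continues, the week-1 saving of 250(7 − *k*) mg is used up after 250(7 − *k*)/1,250 weeks of the weekly phase, at most 1,750/1,250 = 1.4 weeks. For a switch after one 500 mg dose:

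- End of week 2: 2,000 + 1,750 = 3,750 mg against 4,000 mg (0.94)
- End of week 3: 5,500 mg against 4,500 mg (1.22)

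On this reading, a participant whose treatment stopped after two weeks would have had slightly less than standard. One who stopped after three weeks would have had more.

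**The case against.** The strongest reply is that the sentence is plainly about week 1. The exception is a daily amount and only the first week is dosed daily, so a sensible reader substitutes 250 mg for 500 mg in that week and no increase arises. As the more natural reading, this stands. But nothing in the text confines the exception to week 1, and this reading still does not say what happens from day 8.

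A second reply is that the exception halves each single dose under every reading. This also stands. The documents do not say whether GI tolerability follows the single dose or the weekly total. A reader might infer that the provision works against its own purpose, but the documents do not establish that. They support only the statement that the weekly total rises if the exception is used in the weekly phase.

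Third, the pharmacy instructions are not part of the documents and may already settle the schedule. That is possible, and it is why checking them belongs in the remedy. The protocol text would still be open.

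Two stronger readings are tempting:

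- A reader might infer that the Study Stopping Rules contradict the exception, since the same event triggers both. They do not. That section says "Study enrollment will be put on temporary hold and expedited reports will be prepared and reported to the DSMB for an ad hoc meeting", which governs new enrollment and reporting. The exception governs the affected participant's dosing, and both can operate on one event. Equally, the hold does not cure the gap, because it gives no dosing instruction.
- A reader might infer a cardiac hazard from the QTc criteria and the ECG schedule. The documents do not link the exception to QT risk, so that material supports no part of this point.

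**Conclusion.** The point holds as an unresolved dosing instruction and should be fixed. The Treatment Description leaves open the phase in which 250 mg daily applies and whether dosing returns to the weekly schedule, and no other section closes the gap. It is more than missing detail, because a provision offered for intolerance would, applied as written after week 1, give 3.5 times the standard weekly amount, and the weekly phase is most of the treatment period.

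The 0.5 ratio per day in week 1, the 3.5 ratio per week and the 1,250 mg weekly excess follow exactly from the protocol's own figures. The course totals rest on the assumed 8 to 13 weeks. The upper range also requires daily use to continue to the end of treatment, so it is a limiting case and not a forecast.

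A reader might infer from that range that the trial's safety or efficacy results would be distorted. The documents do not support this: they give no expected number of users, so no trial-level effect can be derived.

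**What to change.** The sponsor's clinical team should reconcile the two dosing sentences of the Treatment Description. The clarified text should state the phase or phases in which the allowance applies, and whether and when dosing returns to the weekly schedule. The team should then check that the Research Pharmacy instructions for the chloroquine and placebo arms agree with that text, so that the allowance works the same way in both under blinding. Which schedule is right is a clinical decision; no dose or clinical rule is proposed here.

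The cost is one clarifying sentence and one check of the pharmacy instructions. Sample size, visits and analysis do not change.

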### **Statistical analysis**

Summary statistics for outcomes and predictor variables will be calculated, with comparisons made using Student's t-test and Wilcoxon rank-sum test for normally and non-normally distributed continuous variables, respectively. Counts and percentages will be calculated for categorical variables and compared using  $\chi^2$  or Fisher's exact test as appropriate. COVID disease status will be ascertained based on medical records review for severe hospitalized patients, self-reported history of viral illness with serological confirmation of anti-COVID status, and anti-COVID antibody status. The association between CQ and disease will be explored. Efficacy analyses included all the patients who underwent randomization and who received at least one dose of CQ or placebo (modified intention-to-treat population). The primary end point, the percentage of patients with COVID infection at study end, will be compared in the CQ group and in the placebo group with the use of a stratified Cochran–Mantel–Haenszel test, with strata corresponding to the stratification factors (age and exposure levels). To isolate the association between CQ and possible confounders we will define as those variables associated with both the outcome and the independent variable (CQ). Statistical calculations will be performed using STATA version 12. A two-tailed  $\alpha$  of 0.05 was defined as the level of statistical significance for all tests.

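### Severe illness is labelled co-primary, but the rest of the plan has one primary endpoint and gives no success rule, alpha allocation, placebo rate or power for it

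*Combined protocol and SAP*

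**What the plan says.** The combined protocol and SAP has a Primary Endpoint entry (symptomatic illness, 15% falling to 5%) and a separate Co-primary Endpoint entry: "Decrease by 70% in number of severe illness in at risk healthcare workers". The other relevant places are these.

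- **Primary Objective:** efficacy in health care workers "with moderate to high risk of exposure to COVID-19 in preventing symptomatic COVID-19 infections". Severe illness is not mentioned.
- **Sample size:** "Sample size based on a projection that 15% of healthcare workers will develop symptomatic COVID-19 illness", with 5% expected on chloroquine. The 175 per group "will permit detection of a difference of this magnitude or greater for the primary endpoint", in the singular. The section adds: "The trial is not powered on any secondary outcomes or interim analyses".
- **Statistical analysis:** one endpoint receives the stratified Cochran–Mantel–Haenszel (CMH) test: "The primary end point, the percentage of patients with COVID infection at study end". A two-tailed level "of 0.05 was defined as the level of statistical significance for all tests". Severe cases appear only in the sentence on ascertainment, as hospitalised patients whose records are reviewed. The only test that could apply to them is the generic chi-square or Fisher default for categorical variables.
- **Secondary Objectives:** "the efficacy of CQ in preventing any infection as defined by seroconversion to positive anti-COVID antibody status".

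**The concern.** Co-primary is a statement about the decision rule, and this plan gives no rule to go with it. Three readings are possible:

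1. Either endpoint suffices for success.
2. Both endpoints are required.
3. Symptomatic illness alone decides, and the label is a slip.

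Under reading 1, two tests at 0.05 give two chances of a false positive. Under reading 2, the stated 80% power does not describe the trial's main claim, because it was calculated for symptomatic illness only. Under reading 3, neither error nor power is affected. If the choice is left open until the data are seen, the same result can be reported as a success or a failure.

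A related ambiguity makes this worse. The analysis section calls its primary endpoint COVID infection, which is closer to the seroconversion outcome of the secondary objective than to the symptomatic illness for which the trial was sized.

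**Working it through.** **Inputs from the documents.** Symptomatic illness 15% against 5%; severe illness reduced by 70%; 175 per group; 10% dropout; 1:1 allocation; two-tailed 0.05; 80% power.

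**Step 1: reproduce the plan's figure.** For two proportions with p1 = 0.15, p2 = 0.05 and mean p = 0.10,

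n = [1.960 × √(2 × 0.10 × 0.90) + 0.842 × √(0.15 × 0.85 + 0.05 × 0.95)]² / 0.10² = 141 per group.

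The continuity correction raises this to 160. Allowing for dropout gives 160/0.90 = 178, or 160 × 1.10 = 176, which matches 175 closely. The stated size is therefore explained by symptomatic illness alone. Severe illness plays no part in it.

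**Step 2: assumptions for severe illness.** The documents give no placebo severe rate s, so these are assumptions.

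- s = 1% to 5%, with 10% also shown; 0.3 × s on chloroquine.
- Severe cases are a subset of symptomatic cases.
- 175 × 0.90 = 157 evaluable per arm.
- Symptomatic illness is tested by uncorrected chi-square, unstratified, as an approximation to the CMH test.
- For severe illness, the plan's chi-square or Fisher choice is read as chi-square when the pooled expected count per arm is at least 5, otherwise Fisher.

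The pooled expected count at the planned effects is 157 × (s + 0.3s)/2 = 1.0 per arm at s = 1% and 5.1 at s = 5%. Under the null it is 157 × s = 1.6 and 7.9.

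**Step 3: the three readings.** One million simulated trials were run per cell. The null has 15% symptomatic and equal severe rates in both arms. The alternative has the planned effects.

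Reading 3 (symptomatic alone, exact): error 4.9%, power 86.1%.

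| Placebo severe rate (assumed) | 1% | 2% | 3% | 5% | 10% |
|---|---|---|---|---|---|
| Reading 1, family-wise error | 5.1% | 6.1% | 7.5% | 8.7% | 7.8% |
| – Fisher always | 5.1% | 6.0% | 6.5% | 6.8% | 6.5% |
| – chi-square always | 7.8% | 9.0% | 8.8% | 8.8% | 7.8% |
| Reading 2, joint power | 0.3% | 4.3% | 12.6% | 35.1% | 70.3% |
| – Fisher always | 0.3% | 4.2% | 11.8% | 28.1% | 63.7% |
| – chi-square always | 4.4% | 15.7% | 23.8% | 39.4% | 70.4% |
| Symptomatic significant, severe not | 85.8% | 81.9% | 73.5% | 51.1% | 15.8% |

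The last row counts trials that succeed under reading 3 and fail under reading 2.

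**Step 4: when would reading 2 keep 80% power?** Joint power reaches 80% at s of about 12.5% with chi-square (12.5/15 = 83% of symptomatic placebo cases) or 13.6% with Fisher (13.6/15 = 91%).

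**Step 5: sensitivity to the denominator.** If all 175 per arm are analysed, the five default-rule errors are 5.4, 6.7, 8.2, 8.9 and 7.8%. Joint power is 0.5, 5.9, 16.3, 41.6 and 75.7%. The share with symptomatic significant and severe not runs from 89% at s = 1% to 48% at 5%, and is 14% at 10%. The 80% threshold moves to about 11.1% (chi-square) or 12.3% (Fisher).

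**The case against.** The strongest reply is that the plan is a single-primary trial in all but one label. The objective, the sample size and the analysis section agree on that, and then error and power are as stated. This is right about the likeliest reading. It does not remove the need to correct the label, because the protocol states it under its own heading and a results report could rely on it. The sentence disclaiming power does not help, since it covers secondary outcomes and interim analyses, and a co-primary endpoint is neither.

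A second reply is that the magnitudes depend on severe rates the documents do not give. That also stands. Joint power from 0.3% to 70% shows that the plan cannot fix the size of the problem, and at a 1% rate the excess error under reading 1 is only 0.1 points with the default rule. The figures are conditional illustrations and do not demonstrate an error or power failure in this trial.

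Third, the analysis set is everyone randomised who took at least one dose, so 157 may be too low. Using 175 does not change the conclusion.

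Finally, the mismatch between COVID infection and symptomatic illness is strictly a separate inconsistency about the definition of the primary endpoint. It is included because the same edit must settle which endpoint carries the claim.

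**Conclusion.** The concern holds. The co-primary label has no decision rule, alpha allocation, placebo rate or power behind it, and the other sections treat symptomatic illness as the only endpoint that was sized. Under the likeliest reading the correction is one of labelling. Under the other two readings, either the 5% error rate is exceeded (by up to about 4 points) or the 80% power claim fails unless most symptomatic placebo cases are severe. These sizes rest on the assumed severe rates, on nesting of severe within symptomatic cases, and on unstratified tests. The absence of a rule does not depend on any of them. It should be fixed, although the design itself is not invalidated.

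**What to change.** State which endpoint carries the claim, in a dated amendment before unblinding. The option that matches the objective and the sample size is as follows.

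- Make symptomatic COVID-19 the sole primary endpoint at two-sided 0.05.
- In Statistical analysis, have the CMH test compare the proportion of participants with symptomatic COVID-19 by study end, in place of COVID infection.
- Relabel severe illness as a key secondary endpoint, tested only if the primary is significant. Define it, name its test, and report the estimate with a 95% confidence interval.
- State that its power is low: over assumed placebo rates of 1% to 5% with 157 per arm, 0.3% to 29% by Fisher and 5% to 41% by chi-square.

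If severe illness is to remain co-primary, state the either/both rule, the alpha allocation, the assumed placebo rate and the resulting power, and limit the 80% statement to symptomatic illness.

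The recommended change is to wording only, though the protocol is IRB-approved and the amendment needs the same approval. It adds no participants and leaves symptomatic power at 86%. The price is that severe illness cannot be claimed if the primary fails. At the planned effects, severe illness is significant and symptomatic illness is not in 0.2% to 1.5% of trials by chi-square (0.01% to 0.8% by Fisher) at severe rates of 1% to 5%, and in 2.6% (1.6%) at 10%. The loss is larger if the symptomatic effect is smaller than planned. By comparison, testing each endpoint at 0.025 would cut symptomatic power to 78% (chi-square) or 73% (Fisher) at 157 per arm, or 83% or 79% at 175.
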